## Study Protocol

**Title:** Non-Invasive Detection of Aspergillosis in Ventilated Patients: A Study on the Diagnostic Utility of Galactomannan Analysis in Exhaled Breath Condensate

**Objective:** Evaluate the effectiveness of measuring galactomannan (GM) levels in exhaled breath condensate (EBC) as a non-invasive method for diagnosing Invasive Aspergillosis Pneumonia (IPA) in mechanically ventilated patients.

**Background:** Given the high mortality rates associated with IPA in critically ill patients, timely and accurate diagnosis is paramount. Traditional methods, such as the analysis of bronchoalveolar lavage fluid (BALF), while effective, are invasive and pose risks to patients. This study explores the potential of EBC as a safer alternative.

### Methodology:

- **Study Design:** Comparative analysis of GM levels in EBC and BALF from both a rat model and mechanically ventilated IPA patients.
- **Participants:** 75 mechanically ventilated patients suspected of IPA, with informed consent obtained.
- **Procedures:**
  - Use of a novel EBC collection device for sample gathering.
  - Comparison of GM levels in EBC and BALF, alongside cytokine profiles.
- **Ethics Approval:** Granted by the Medical Ethics Committee of Sichuan Provincial People's Hospital.

## Statistical Analysis Plan

### Data Analysis Strategy:

1. **Descriptive Statistics:**
  - Summarize participant characteristics using means and standard deviations for continuous variables and frequencies for categorical variables.
2. **Diagnostic Marker Evaluation:**
  - Perform logistic regression to evaluate the diagnostic utility of GM levels in EBC and BALF.
  - Receiver Operating Characteristic (ROC) curve analysis to determine the diagnostic effectiveness, identifying optimal cutoff values for sensitivity and specificity.
3. **Comparison Between Groups:**
  - Use t-tests or Mann-Whitney U tests for continuous variables and chi-square tests for categorical variables to compare the IPA and control groups across different measures (e.g., GM levels, cytokine profiles).
4. **Correlation Analysis:**
  - Assess the relationship between EBC-GM and BALF-GM levels using Pearson's or Spearman's correlation coefficients, depending on data distribution.
5. **Threshold Analysis:**
  - Determine a specific cutoff value for EBC-GM that maximizes diagnostic accuracy, focusing on sensitivity, specificity, and the Area Under the Curve (AUC) from ROC analysis.

**Software:** Statistical analysis will be conducted using SPSS version 25.0 or a similar statistical package.

**Ethical Considerations:** Data will be anonymized to protect patient confidentiality, with all procedures carried out in accordance with the Declaration of Helsinki.

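### The SAP plans no paired EBC-minus-BALF accuracy difference with a confidence interval, and the planned correlation cannot stand in for one

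*Combined protocol and SAP*

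**What the plan says.** The Background describes lavage as effective but invasive and adds: "This study explores the potential of EBC as a safer alternative". Under Methodology, the study design is "Comparative analysis of GM levels in EBC and BALF from both a rat model and mechanically ventilated IPA patients", and the procedures list "Comparison of GM levels in EBC and BALF, alongside cytokine profiles". The participants are "75 mechanically ventilated patients suspected of IPA, with informed consent obtained".

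In the SAP's Data Analysis Strategy:

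- Item 2 says "Perform logistic regression to evaluate the diagnostic utility of GM levels in EBC and BALF" and adds ROC analysis with cutoffs. It does not mention comparing the two curves.
- Item 3 tests IPA against control patients, not EBC against BALF.
- Item 4, on correlation, reads: "Assess the relationship between EBC-GM and BALF-GM levels using Pearson's or Spearman's correlation coefficients, depending on data distribution". It names no analysis set.
- Item 5 looks for a cutoff for EBC-GM only.

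The SAP names no confidence interval for any estimate, no paired test and no margin.

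**The concern.** The written objective is the diagnostic value of EBC-GM, and items 2 and 5 address it. The Background and the comparative design raise a second question: how much accuracy is lost or kept if EBC replaces BALF? For that question the plan yields, at best, two separate AUCs and a correlation coefficient. Subtracting the AUCs gives a point difference. Its uncertainty needs their covariance, which separate ROC analyses do not supply. The coefficient measures something else, because it mixes how well each marker separates the groups with how the markers move together within a group.

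Item 4 is also open as to whom it covers. The Methodology names a rat model, IPA patients and patients with suspected IPA, and item 3 adds a control group. If IPA and control patients are pooled, group separation alone produces a positive correlation, which could be read as evidence that EBC can replace BALF.

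**Working it through.** **Inputs.** From the documents: 75 patients. They give no AUC, IPA/control split, number of pairs or margin, so there is no planned figure to reproduce. Everything else here is an assumption: normal markers with equal variance in both groups, separation d = √2·Φ⁻¹(AUC), 30 IPA and 45 control patients (IPA share p = 0.4) unless stated, and within-group correlation ρ of 0.3 or 0.5.

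**1. What a pooled correlation contains.** With k = p(1−p),

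r = (ρ + k·d_E·d_B) / √[(1 + k·d_E²)(1 + k·d_B²)].

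The formula is symmetric in d_E and d_B, so exchanging the two AUCs leaves r unchanged. It cannot show which marker is better.

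**2. One coefficient, many gaps.** Fix r = 0.70 and p = 0.3 (k = 0.21), and solve for ρ:

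- AUCs 0.85 and 0.85 (d² = 2.148): ρ = 0.70 × 1.451 − 0.451 = 0.565.
- AUCs 0.90 and 0.80 (d = 1.812 and 1.190): ρ = 0.70 × √(1.690 × 1.297) − 0.453 = 0.583.
- AUCs 0.95 and 0.75: ρ = 0.651.

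All three values are admissible, so r = 0.70 fits gaps of 0, 0.10 and 0.20 in either direction.

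**3. Spearman coefficient at this sample size.** BALF AUC 0.95, 30/45, simulated studies:

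| EBC AUC | Gap | ρ | Mean Spearman | Central 95% of studies |
|---|---|---|---|---|
| 0.95 | 0 | 0.3 | 0.70 | 0.58 to 0.80 |
| 0.90 | 0.05 | 0.3 | 0.65 | |
| 0.85 | 0.10 | 0.5 | 0.70 | |
| 0.80 | 0.15 | 0.5 | 0.65 | 0.50 to 0.78 |

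If ρ is held at 0.5, the coefficient does fall, from 0.78 to 0.65, as the EBC AUC drops from 0.95 to 0.80. But two equal AUCs of 0.80 give 0.61, lower than the 0.15 gap does.

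**4. Correlation from pooling alone.** With ρ = 0 and equal AUCs, r = q/(1 + q), where q = p(1−p)d² = 0.24·d²:

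- AUC 0.80: q = 0.340, r = 0.25
- AUC 0.85: q = 0.516, r = 0.34
- AUC 0.90: q = 0.788, r = 0.44
- AUC 0.95: q = 1.299, r = 0.56

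**5. What the paired difference would deliver.** Mean 95% half-width (1.96 × paired DeLong standard error), for ρ = 0.3 / 0.5 at 30/45:

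- 0.80 vs 0.80: 0.124 / 0.107
- 0.90 vs 0.80: 0.109 / 0.097
- 0.95 vs 0.80: 0.102 / 0.094
- 0.90 vs 0.85: 0.099 / 0.087
- 0.95 vs 0.95: 0.059 / 0.052

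The overall range is 0.05 to 0.12 at 30/45, 0.06 to 0.14 at 20/55, and 0.06 to 0.15 if only 50 patients (20/30) have both specimens. As an example of what pairing gains, with 25 IPA cases, both AUCs 0.85 and ρ = 0.5, the half-width is 0.097 using the covariance and 0.128 ignoring it.

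Chance that the 95% interval excludes zero:

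- 0.95 vs 0.80: 87–94% at 30/45 and 68–79% at 20/30.
- 0.90 vs 0.80: 43–54% at 30/45, 37–44% at 20/55 and 29–36% at 20/30.
- 0.90 vs 0.85: below 20% in all three.

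**6. If BALF-GM helps define IPA.** Assume truly equal AUCs of 0.80 to 0.90, 40% IPA, BALF-GM called positive above the control 80th percentile, and a random share of labels set by BALF-GM. The apparent EBC-minus-BALF difference is then −0.03 to −0.065 at a 25% share and −0.07 to −0.13 at 50%.

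**The case against.** The strongest reply is that the plan never promises a comparison of accuracy. The objective concerns EBC-GM alone, the Methodology compares levels, and the remark about a safer alternative is an exploratory Background sentence. No equivalence or non-inferiority claim is made. Item 4 does not say its coefficient will support a statement on relative accuracy, and a reader could subtract the two AUCs from item 2. The example in step 3 also depends on changing ρ between rows. Finally, the proposed interval may prove inconclusive, or only descriptive if BALF-GM is part of the reference standard.

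Much of this stands, and it limits the weight of the point. The comparison is secondary to the stated objective, and the degree of overlap in step 3 comes from assumed values. It does not remove the gap. Levels in two different fluids do not show whether one test can replace the other, and replacement is the reason given for studying EBC. Two AUCs without their covariance give no interval. Because ρ is unknown beforehand, letting it vary is the realistic case. A wide interval would show the uncertainty that a coefficient hides.

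**Conclusion.** The concern holds and should be fixed. It does not undermine the stated objective, which items 2 and 5 address. The plan has no estimate with an interval for accuracy lost or kept relative to BALF, and the correlation cannot supply one: similar coefficients are compatible with no gap and with a 0.15 AUC gap.

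That the correlation does not identify the difference follows from the formula. The sizes rest on binormal markers and on assumed AUCs, case splits and within-group correlations. On those assumptions, 75 pairs would usually reveal a gap as large as 0.95 vs 0.80, but would leave 0.90 vs 0.80 near even odds and smaller gaps unresolved. The result can be read as a fair comparison only if BALF-GM plays no part in defining IPA, and the documents do not state how IPA is defined.

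**What to change.** - **Item 2:** add the paired AUC difference, EBC-GM minus BALF-GM, in human patients with both specimens. Give a 95% CI by DeLong or patient-level bootstrap and the number of pairs. Paired sensitivity and specificity differences at each marker's cutoff can be added, using a bootstrap that repeats the cutoff selection.
- **Reference standard:** state how IPA is defined and whether BALF-GM contributes. If it does not, base statements on accuracy relative to BALF on this interval. If it does, say that the comparison favours BALF and treat it as descriptive.
- **Item 4:** state the analysis set, and report the correlation separately in the IPA and control groups, or adjusted for group, as supportive only.

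The cost is SAP wording and standard paired-ROC code. Patients who already give both specimens need no further sampling. The reference standard has to be written down first. The price in interpretation is that the interval may be inconclusive, and that within-group correlations will be imprecise in the smaller group.

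### The EBC-GM cutoff is chosen and judged in the same patients, with no validation or correction, so its sensitivity and specificity will be too high on average

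*Combined protocol and SAP*

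**What the plan says.** SAP, Data Analysis Strategy, item 5 (Threshold Analysis) is the main source: "Determine a specific cutoff value for EBC-GM that maximizes diagnostic accuracy, focusing on sensitivity, specificity, and the Area Under the Curve (AUC"). Item 2 (Diagnostic Marker Evaluation) adds a ROC analysis "identifying optimal cutoff values for sensitivity and specificity", without naming the marker. It also says: "Perform logistic regression to evaluate the diagnostic utility of GM levels in EBC and BALF", without stating whether the two are modelled jointly or separately.

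The Methodology section of the protocol describes one human cohort, "75 mechanically ventilated patients suspected of IPA". Its Study Design entry shows that the only other data are from animals: "Comparative analysis of GM levels in EBC and BALF from both a rat model and mechanically ventilated IPA patients". Item 3 uses tests "to compare the IPA and control groups across different measures", but the documents give no group sizes and do not say whether the controls are among the 75.

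Nothing in the protocol or SAP mentions a cutoff fixed in advance, a validation cohort, a sample split, cross-validation, a bootstrap, or confidence intervals for sensitivity and specificity.

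**The concern.** A search over all cutoffs picks the one that suits the chance pattern of these particular patients. Scoring that cutoff in the same patients counts the chance pattern as performance, so apparent sensitivity and specificity exceed, on average, what the cutoff would achieve in new patients.

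The criterion is also open. Diagnostic accuracy could mean the Youden index (sensitivity + specificity − 1) or the proportion correctly classified, and these can give quite different cutoffs. AUC cannot choose a cutoff because it does not depend on one. An open criterion can also be settled after the data are seen.

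The stated objective is to "Evaluate the effectiveness of measuring galactomannan (GM) levels in exhaled breath condensate (EBC") for diagnosing IPA. The cutoff with its sensitivity and specificity is a named output, and it is what a reader would use to judge EBC against BALF. Deriving a cutoff at this stage is reasonable; the gap is reporting its performance uncorrected.

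**Working it through.** **Inputs.** From the documents: 75 patients and a data-driven cutoff. The documents give no sample-size derivation or expected accuracy, so there is no figure of the plan's own to reproduce. Everything else is assumed: the case/control split, true AUC, marker distribution and criterion.

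**Model.** Controls are N(0, 1); IPA cases are N(μ, s) with SD s = 1, 2 or 3. Then AUC = Φ(μ/√(1 + s²)), so μ = √(1 + s²) × Φ⁻¹(AUC). At cutoff c, true sensitivity is 1 − Φ((c − μ)/s) and true specificity is Φ(c). Optimism is the mean apparent value minus the mean true value at the same chosen cutoff.

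**One case.** Take 25 IPA, 50 controls, AUC 0.80, equal SDs and a Youden cutoff, so μ = 1.414 × 0.842 = 1.19.
- Sensitivity: apparent 0.773, true 0.704, optimism +6.8 points (from unrounded means).
- Specificity: apparent 0.753, true 0.719, optimism +3.4 points.
- Sum: 0.068 + 0.034 = 0.102.

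**Direction.** Forty scenarios were run with 6,000 studies each: five splits from 15/60 to 60/15, AUC 0.70 to 0.95, equal SDs, and either the Youden index or the proportion correct maximised. Both measures were too high on average in all 40, and the sum was too high by 0.066 to 0.141. With a cutoff fixed beforehand, bias in the sum was −0.002 to +0.002.

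**Size.** Youden cutoff, AUC 0.75 to 0.90, 4,000 studies per setting:

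| Setting | Sensitivity + specificity overstated by |
|---|---|
| 15, 25 or 38 IPA of 75, equal SDs | 0.080 to 0.135 |
| Same, IPA SD twice the control SD | 0.068 to 0.110 |
| Same, IPA SD three times the control SD | 0.052 to 0.090 |
| Same, assay floor 0.5 SD above the control mean | 0.073 to 0.100 |
| 50 or 60 IPA of 75 | 0.061 to 0.136 |
| 75 IPA plus 75 separate controls | 0.037 to 0.068 |

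Repeat runs gave 0.053 to 0.138 within the 75 and 0.036 to 0.069 for 75 plus 75. The smaller group's measure is inflated more: 6.3 to 10.7 points in a group of 15, 3.9 to 7.4 in a group of 25, and 2.6 to 5.1 each with equal groups. If the proportion correct is maximised instead, that proportion is overstated by 2 to 5 points.

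**Criterion.** With 25 IPA, AUC 0.85 and equal SDs, mean true sensitivity/specificity is 76%/75% under Youden and 63%/86% under the proportion correct, taking the lowest of tied cutoffs. Breaking ties at random gives about 75%/76% and 60%/87%. With a threefold SD the pairs are 72%/92% and 69%/95% (lowest tied cutoff).

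**Against sampling error.** With 25 cases and sensitivity 0.75, the 95% half-width is 1.96 × √(0.75 × 0.25/25) = 0.17. The bias is smaller than this, but an ordinary 95% interval for the apparent sum covered the true value in only 71% to 87% of studies.

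**AUC.** The AUC of EBC-GM alone was within 0.004 of the truth. A joint EBC plus BALF logistic model had an AUC too high by 0.006 to 0.016.

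**Does correction work?** Stratified 10-fold cross-validation with 5 repeats was tried in 27 settings (15, 25, 38 IPA; AUC 0.75, 0.85, 0.90; s = 1, 2, 3).
- Bias left in the sum was −0.003 to +0.004 (repeat runs in fewer settings: −0.010 to +0.007), and at most 1.8 points in either measure.
- Root-mean-square error of the sum fell in all 27, by 0.004 to 0.025. For sensitivity alone it changed by −0.3 to +1.5 points; for specificity alone it rose by 0.3 to 1.9 points.
- Intervals that resample patients and rerun the whole cross-validation covered 95% to 99% for the sum, 92% to 98% for specificity and 86% to 97% for sensitivity (lowest with 15 IPA and AUC 0.90). Monte Carlo error is 1 to 2 points.
- Bootstrap optimism correction removed only 60% to 71% of the bias.

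**The case against.** - **The data set is inferred.** Item 5 does not name the data it will use, and a cutoff set in rats and only tested in patients would escape the bias. The text gives no support for that reading, and the 75 patients are the natural one.
- **The size is assumed.** Across the assumed settings the sum's overstatement runs from 0.037 to 0.136, almost fourfold. This stands: only the direction is firm.
- **The 75% to 90% frequency is for the sum under Youden.** In one set of runs sensitivity alone was overstated in 59% to 87% of studies and specificity alone in 69% to 92%. When the proportion correct was maximised with 60 IPA, 15 controls and AUC 0.75, the sum was overstated in only 51% (SD ratio 2) or 57% (SD ratio 3). There the rule often calls nearly everyone positive, and the share depends on how such cutoffs are counted. The average bias stayed positive throughout.
- **The remedy has costs.** Each measure taken alone becomes somewhat noisier, sensitivity intervals can fall short of 95%, and cross-validation assesses the selection procedure rather than the single published cutoff. These points stand and should be stated in the report. They do not favour the uncorrected figure, whose error runs in one direction on average.
- **The wording of item 5.** Its mention of AUC may only list measures to report. That is possible, and one sentence in the SAP would settle it.
- **The study is exploratory.** The Background says: "This study explores the potential of EBC as a safer alternative". This justifies deriving a cutoff and limits the weight of the point. It does not justify reporting the cutoff's performance uncorrected.

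**Conclusion.** The concern holds. Followed as written, the plan yields sensitivity and specificity that are biased upwards on average, and this is more than missing detail. The direction is well supported: it appeared under both criteria and every split, AUC and marker shape tried. The size is conditional. The sum is overstated by about 0.05 to 0.14 if cases and controls together make up the 75, and by about 0.04 to 0.07 if 75 controls are added, for a true AUC of 0.75 to 0.90 and a Youden cutoff. The AUC of EBC-GM alone is sound. This should be fixed before analysis, but it does not invalidate the study.

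**What to change.** Amend item 5, and item 2 for any cutoff derived there, including one for BALF-GM:

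1. Name one cutoff criterion before the data are analysed, for example the Youden index, with a rule for ties. Drop AUC as a means of choosing a cutoff.
2. Report sensitivity and specificity both as apparent and as cross-validated values (10-fold, stratified by IPA status, repeated, with the cutoff search redone in each training part). Base conclusions on the corrected values. Bootstrap optimism correction is acceptable if labelled partial.
3. Give 95% intervals that include the cutoff search: resample patients, rerun the whole cross-validation in each resample with copies of a patient kept in one fold, and take percentiles.
4. If a logistic model combines markers, correct its AUC in the same way.
5. State that the cutoff is exploratory until confirmed in new patients.

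The cost is a few lines of SAP text and a short program, with no new patients, samples or procedures. The Software clause already allows a package other than SPSS. The interval in step 3 is the most demanding part to program. Reported performance will fall by roughly the amounts in the verdict, and the separate corrected measures will be less biased but somewhat more variable.
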